### 8.2.3 Time to first seizure

The time to the first seizure (days) will be calculated as:

Date of first seizure in the trial – date of first BRV administration + 1

If the exact date of first seizure cannot be determined but the patient has had seizures recorded post Visit 1, then the patient will still be counted as having an event using a conservative approach as shown in [Table 8–2](#).

For patients with no evidence of seizures, the following sequential approach will be taken which is further detailed in [Table 8–2](#):

1. For patients attending a visit but with missing seizure data, they will be censored at the date of the last visit prior to the visit with the missing seizure information.
2. For patients discontinuing BRV study medication before experiencing their first seizure, they will be censored at the date of last administration of BRV while in the study.
3. For patients with no recorded seizures and still on BRV study medication, they will be censored at the date of last visit.

As the approach used is very conservative, if there are a lot of patients censored in the early visits due to missing data or with early events due to missing data, a sensitivity analysis may be performed.

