### **4.2 Secondary variables**

The following secondary variables will be measured:

- BRV retention at 3 months
- BRV retention at 6 months
- Absolute reduction in POS frequency (seizures per 28 days) from Baseline to 3 months
- Absolute reduction in POS frequency (seizures per 28 days) from Baseline to 6 months
- Absolute reduction in POS frequency (seizures per 28 days) from Baseline to 12 months

- Absolute reduction in POS frequency (seizures per 28 days) from Baseline to end of Observation Period
- Percent reduction in POS frequency (seizures per 28 days) from Baseline to 3 months
- Percent reduction in POS frequency (seizures per 28 days) from Baseline to 6 months
- Percent reduction in POS frequency (seizures per 28 days) from Baseline to 12 months
- Percent reduction in POS frequency (seizures per 28 days) from Baseline to end of Observation Period
- Response based on percent reduction in POS (seizures per 28 days) at 3 months (response is a reduction of  $\geq 50\%$ )
- Response based on percent reduction in POS (seizures per 28 days) at 6 months (response is a reduction of  $\geq 50\%$ )
- Response based on percent reduction in POS (seizures per 28 days) at 12 months (response is a reduction of  $\geq 50\%$ )
- Response based on percent reduction in POS (seizures per 28 days) at end of Observation Period (response is a reduction of  $\geq 50\%$ )
- Seizure freedom at 3 months
- Seizure freedom at 6 months
- Seizure freedom at 12 months
- Seizure freedom at end of Observation Period
- Time to first seizure after first dose of BRV

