**Table 17–1: Recommended schedule of study assessments**

Assessments	Visit 1 a Baseline/Day 1 First Day of BRV Treatment	Visit 2 3 Months (Approximately 3 months after Baseline according to routine practice b )	Visit 3 6 Months (Approximately 6 months after Baseline according to routine practice b )	Visit 4 c 12 Months (Approximately 12 months after Baseline according to routine practice b ) End of Observation/ Withdrawal Visit
Recording of AEs	X h	X	X	X
QOLIE-31-P	X	X	X	X
EpiTrack cognition assessment	X		X	X
CGIC		X	X	X
PGIC		X	X	X
Withdrawal criteria		X	X	
Study termination				X

AE=adverse event; AED=antiepileptic drug; BRV=brivaracetam; CGIC=Clinical Global Impression of Change; PGIC= Patient’s Global Impression of Change; QOLIE-31-P=Patient Weighted Quality of Life in Epilepsy Inventory-Form 31

a Visit 1 will be performed after the decision is taken to start adjunctive BRV therapy. Treatment with BRV should be initiated according to routine clinical practice. If the first dose of BRV is given on the same day as Visit 1, it should be administered after Baseline assessments are complete.

b The frequency of visits after Visit 1 will be based on local clinical practice and the patients’ requirements. The clinical procedures performed at each visit will also follow local clinical practice.

c For patients who discontinue early, the treating physician should collect data as specified for Visit 4 as a Withdrawal Visit.

d To include year of first epilepsy diagnosis, lifetime AEDs, etiology. Dates of use of levetiracetam with dosages and reason for discontinuation will be recorded when applicable.

e The treating physician will explain the importance of diary completion to the patient and will review his/her diary at each visit.

f The treating physician will evaluate at each visit the frequency and type of seizures experienced by the patient since the previous study visit. At Baseline, seizure frequency will be based on the previous 3 months to estimate the frequency per 28 days.

g Record name of AED and dose, and any changes after Visit 1.

h Adverse events will be recorded from the moment data consent is obtained.

---

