### **2.3 Study design and conduct**

EP0077 is a postmarketing, multinational, multicenter, prospective noninterventive study (NIS) conducted at approximately 100 sites in approximately 10 European countries, with a 12-month Observation Period. Brivaracetam will be prescribed according to normal clinical practice and in accordance with the current summary of product characteristics (SmPC) in Europe for BRV. It is planned to include 530 patients in the study.

The patients will be followed as per current clinical practice. No additional clinical diagnostic or monitoring procedures will be applied. The use of an epilepsy/seizure diary, as standard clinical practice, is a requirement to enter the study. The selected questionnaires will be used if part of the standard clinical practice at the sites for the management of patients with epilepsy. The choice of medical treatment is made independently by the treating physician in the regular course of practice and is not influenced by the NIS protocol.

The clinical evaluation of patients with epilepsy will be performed by the treating physician following routine clinical practice. All visits and assessments will be scheduled and conducted per routine clinical practice. It is anticipated that each patient will have approximately 4 visits during their participation in this study. These visits will consist of:

- Visit 1, Baseline, Day 1: represents the first day of BRV treatment
- Visit 2, approximately 3 months after Baseline
- Visit 3, approximately 6 months after Baseline
- Visit 4, approximately 12 months after Baseline or end of Observation Period

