### 8.2.2.2 Derivation of seizure frequency related variables

The following variables will be defined for each visit and Month 12 /Withdrawal using the 28-day Baseline and 28-day post-Baseline seizure frequency variables described in [Section 8.2.2.1](#).

- Absolute reduction in POS frequency defined as:  
$$28\text{-day Baseline} - 28\text{-day post-Baseline seizure frequency}$$
- Percent reduction in POS frequency defined as:  
$$\frac{28\text{-day Baseline} - 28\text{-day post-Baseline seizure frequency}}{28\text{-day Baseline}} \times 100$$
- Patients with 0 POS at Baseline will be excluded from the analysis of percent reduction and response ( $\geq 50\%$ ).
- Response (Yes, No) where Yes is  $\geq 50\%$  reduction in POS frequency calculated as described above and No otherwise.
- Seizure freedom (Yes, No) will be defined using 2 methods as shown in [Table 8-1](#). The first method considers patients who withdraw prior to their 1st seizure as Not seizure free. The 2nd is a less conservative method which considers patients who withdraw prior to their 1st seizure as missing. Visit 4 (Month 12/Withdrawal) will not be summarized for seizure freedom.

Table 8–1: Derivation of seizure freedom		
Patient Classification at Visit (patients are assigned to the first category they fall into)	Seizure freedom – Discontinuations counted as not seizure free	Seizure freedom – Discontinuations counted as missing
0. Patients had a seizure before 1st BRV dose	Missing	Missing
1. Patient had a seizure on or after 1st BRV dose and on or before the visit date derived using the following conditions. First_seizure_date = Date of first seizure or if date of first seizure is missing but patient has seizures recorded at a visit, then assign first_seizure_date as the date of the visit prior to the earliest visit with seizures recorded a) Visit date present and First_seizure_date is on or after 1st BRV and on or before the Visit date b) Visit date is missing (either due to patient ongoing in study or visit missed) and First_seizure_date is on or after 1st BRV and on or before the visits target day [a])	No	No
2. Patient discontinued BRV or terminated the study prior to the visit’s target day [a]	No	Missing

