**Table 8–2: Derivation of time to first seizure**

Missing date of first seizure but seizures recorded				No evidence of seizures on the study			
V2	V3	V4	Date used	V2	V3	V4	Date used
M	M	>0	E-V1/1BRV [a]	M	M	M	C-V1
M	>0	NA	E-V1/1BRV [a]	0	M	M	C-V2
>0	NA	NA	E-V1/1BRV	M	0	M	C-V1
0	>0	NA	E-V2	M	M	0	C-V1
0	0	>0	E-V3	0	0	M	C-V3
M	-	>0	E-V1/1BRV [a]	0	M	0	C-V2
0	-	>0	E-V2	M	0	0	C-V1
-	>0	NA	E-V1/1BRV [a]	0	0	0	C-V4
-	M	>0	E-V1/1BRV [a]	0	Disc BRV	NA	C- Last BRV
				M	Disc BRV	NA	C-V1

[a] The rationale behind using V1/1BRV in this scenario is based on it being unknown when exactly between V1 and V4 that the first seizure event occurred. V1/1BRV is more conservative and hence will be used, however a sensitivity analysis may be performed if there are a lot of patients with missing data.

Note: M=patient is missing seizure data at this visit but attended the visit, - = patient missed entire visit, NA=Visit is not applicable/not required to be considered in this scenario, V=Visit, C=Censor, E=Event, 1BRV= Date of first dose of BRV, Last BRV= date of last dose of BRV.

Note: V1/1BRV implies the date of the first dose of BRV should be used if it is later than V1 to avoid negative time to events and under-reporting of potential seizure events. For patients with no evidence of seizures on the study, negative censoring times are acceptable as it is equivalent to censoring the patient on Day 1.

The time to first seizure from the date of first dose of BRV will be analyzed using Kaplan-Meier methods, from which the median time to first seizure (and 95% CI) will be calculated, along with 25% and 75% quartiles (and 95% CI for the quartiles). In addition, the cumulative number of events, number at risk, and survival estimate at monthly intervals will be provided. The Kaplan-Meier plot and raw statistical procedure output will be produced for the Kaplan-Meier analysis. This will be performed on the FAS and the modified FAS.

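### SAP 8.2.3 takes the first seizure in the trial rather than the first seizure on brivaracetam (BRV), so a dated seizure before the first dose gives an event time of zero or less

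*SAP*

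**What the plan says.** The variable and the time origin are clear. Protocol Section 4.2 lists "Time to first seizure after first dose of BRV" as a secondary variable, SAP Section 2.2.2 repeats it, and the text below SAP Table 8–2 says: "The time to first seizure from the date of first dose of BRV will be analyzed using Kaplan-Meier methods".

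The derivation in SAP Section 8.2.3 is "Date of first seizure in the trial – date of first BRV administration + 1". It sets no lower bound at the first dose. The listing in Section 8.2.2.3 likewise carries a single date, that of the first seizure in the study.

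On whether Visit 1 and the first dose can differ, the documents speak both ways. The design text reads "Visit 1, Baseline, Day 1: represents the first day of BRV treatment", and the column header of Protocol Table 17–1 agrees. Footnote a of that table makes same-day dosing conditional: "If the first dose of BRV is given on the same day as Visit 1, it should be administered after Baseline assessments are complete". SAP Table 8–1 opens with a category for "Patients had a seizure before 1st BRV dose" and sets seizure freedom to missing there. The note to Table 8–2 says that the first-dose date "should be used if it is later than V1 to avoid negative time to events".

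**The concern.** The formula and the variable name describe different events whenever a seizure falls between Visit 1 and the first dose. Physicians record seizures since the previous study visit (Protocol Section 11; Table 17–1 footnote f), and seizure dates are documented, so a seizure in that interval can become the first seizure in the trial. Followed literally, the formula then gives a failure at or before the time origin, and the first seizure on treatment plays no part.

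The authors dealt with the neighbouring cases. Undated seizures are floored at the first dose, negative censoring times are explicitly accepted, and seizure freedom has its own pre-dose category. Dated pre-dose seizures are the case left without a rule. The SAP does not say how an event time of zero or less enters the Kaplan-Meier analysis, so two programmers could report different curves, medians and quartiles for the same data.

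**Working it through.** The plan states no event count, median or precision for this variable, so there is no figure to reproduce. The check is of the rule itself.

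**1. The formula around the first dose.** Time = seizure date - first BRV date + 1.

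| Seizure relative to first BRV | Time (days) |
|---|---|
| 14 days before | -13 |
| 7 days before | -6 |
| 5 days before | -4 |
| 1 day before | 0 |
| same day | 1 |
| 1 day after | 2 |

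Every dated pre-dose seizure gives a value of zero or less. Zero does not exist in the SAP's own day numbering, which runs from Day -1 to Day 1 (Section 3.2.1).

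**2. One record, with assumed dates.** Visit 1 on 1 March, seizure on 5 March, first BRV on 10 March, next seizure on 2 April.
- As written: 5 March - 10 March + 1 = -5 + 1 = -4.
- By the variable's definition: 2 April - 10 March + 1 = 23 + 1 = 24.

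**3. Whether another rule catches it.**
- The event side of Table 8–2 covers only patients whose first seizure date is missing. Its floor at first BRV, there "to avoid negative time to events and under-reporting of potential seizure events", therefore does not reach a dated seizure.
- The same note accepts negative times only for patients without any recorded seizure, who are censored.
- Table 8–1 row 1 requires the seizure to be on or after first BRV, but that table derives seizure freedom only.

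No rule covers the dated pre-dose event.

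**4. Scale, for illustration only.** Under an assumed Poisson process with r seizures per 28 days, the chance of at least one seizure in a gap of g days is 1 - exp(-r × g / 28). For example, r = 5 and g = 7 give 1 - exp(-1.25) = 71.3%. The rates 5 and 10 are the cut points of the SAP's Baseline categories; the rate 1 and all gaps are assumptions.

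| Rate per 28 days | 1 day | 3 days | 7 days | 14 days |
|---|---|---|---|---|
| 1 | 3.5% | 10.2% | 22.1% | 39.3% |
| 5 | 16.4% | 41.5% | 71.3% | 91.8% |
| 10 | 30.0% | 65.7% | 91.8% | 99.3% |

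These are chances for a patient who has such a gap. The documents give neither the share of patients with a gap nor its length, so the table does not convert into a number of patients or a shift in the median.

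**The case against.** **The gap is nominally zero.** The design text and the schedule header put Visit 1 on the first BRV day. That stands as the intended schedule, and it may keep the number affected small. It does not close the point, because the SAP itself wrote two rules for a later first dose.

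**The intent is plain.** The variable name and the time origin both point to seizures after the first dose. The + 1 is the form that Section 3.2.1 reserves for days on treatment; under that section the example seizure would be Day -5, not -4. The listing would show the two dates and the derived time together, so a non-positive value could be noticed. All of this is fair, and a careful programmer might add the condition. The SAP still names a different date and does not instruct the condition.

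**Stronger readings that the documents do not support.** A reader might go on to estimate a count: at an assumed 3 seizures per 28 days and a 7-day gap the chance is 1 - exp(-0.75) = 52.8%, and 10% to 30% of 477 patients (530 × 0.9) with such a gap would give 477 × 0.528 × 0.10 to 0.30 = 25 to 76 patients. The rate, the gap and the share are all assumed, and one rate is applied to everyone. With the same mean but gamma-distributed rates (assumed shape 0.5), the chance falls to 1 - (1 + 0.75/0.5)^(-0.5) = 37%.

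A reader might also infer a direction of bias: upward if such patients are dropped, downward if they count as failures at the origin. The documents describe neither handling. With one constant Poisson rate, seizures in the gap say nothing about later ones, so dropping these patients would cause no bias; an upward bias needs rates that differ between patients. Counting 25 or 76 of 477 as failures at zero would move the median from 28 × ln 2 / 3 = 6.5 days to (28/3) × ln(2 × (1 - 25/477)) = 6.0 or (28/3) × ln(2 × (1 - 76/477)) = 4.8 days, but only under those same assumptions.

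Finally, the true first on-treatment seizure is lost for good only if the CRF holds no later seizure date, and the CRF layout is not shown.

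**Conclusion.** The point holds as a defect in a stated rule. Read literally, SAP 8.2.3 gives an event time of zero or less for any patient with a dated seizure between Visit 1 and the first dose, and nothing else in the SAP corrects it. This rests only on the wording and on the documents' own allowance for a first dose after Visit 1; no assumed rate is needed.

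Its size is unknown. It touches only patients who have both a gap and a dated seizure within it, and neither can be counted from the documents. Patient counts, a shift in the median and a direction of bias should not be claimed. The variable is a descriptive secondary one in a single-arm study without inferential analyses, so the primary retention result is unaffected. The correction is still worth making, because it is cheap and the reported times would otherwise depend on an unwritten programming choice.

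**What to change.** In SAP 8.2.3, define the event as the first seizure on or after first BRV administration, with time = that date - date of first BRV administration + 1. The minimum is then 1 day, in line with the condition already used in Table 8–1 row 1. Add what happens when the earliest recorded date precedes first BRV:

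- If the CRF holds later seizure dates, use the first one on or after first BRV.
- If it holds only a pre-BRV date and further seizures are recorded at post-Baseline visits, apply the undated-seizure rows of Table 8–2.
- If it holds only a pre-BRV date and no further seizures are recorded, apply the censoring rules.

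Report the number of patients with a dated pre-BRV seizure, and add a sensitivity analysis that excludes them, matching the missing category in Table 8–1 row 0.

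The cost is one sentence, the fallback text and a small amount of programming, with no new data. The drawback lies in the second case. If only one date is held and further seizures are recorded at Visit 2, Table 8–2 places the event on the first-dose date, so the example patient would get 1 day rather than 24. That is conservative, and how often it happens depends on the CRF. The count and the sensitivity analysis let the reader judge how much it matters.

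### Time to first seizure: a gap in seizure data leads to censoring only if no seizure is recorded later, so the Kaplan-Meier curve is biased

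*SAP*

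**What the plan says.** The variable (SAP 8.2.3) is "Date of first seizure in the trial – date of first BRV administration + 1", analysed by Kaplan-Meier on the FAS and the modified FAS, with median, quartiles and monthly estimates.

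Patients are first divided by whether any seizure is recorded after Visit 1.

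- **A seizure is recorded.** If its exact date cannot be determined, "then the patient will still be counted as having an event using a conservative approach as shown in", the reference being to Table 8-2. There, missing data at V2 (or at V2 and V3) followed by a positive count gives an event at Visit 1 or first dose. The footnote's reason is "based on it being unknown when exactly between V1 and V4 that the first seizure event occurred". A dated seizure simply takes its date.
- **No seizure is recorded at any visit.** Only here does the missing-data rule apply. The list of rules is introduced by "For patients with no evidence of seizures, the following sequential approach will be taken". Its first item then covers a visit attended without seizure data: "they will be censored at the date of the last visit prior to the visit with the missing seizure information". In Table 8-2 the V2/V3/V4 patterns M/0/0, M/0/M and M/M/0 are all censored at Visit 1, and 0/M/0 at Visit 2. The code is defined as "M=patient is missing seizure data at this visit but attended the visit".

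On mitigation, a footnote to Table 8-2 reads "V1/1BRV is more conservative and hence will be used, however a sensitivity analysis may be performed if there are a lot of patients with missing", meaning missing seizure data, and the text of 8.2.3 makes a similar offer. Neither gives a trigger or a method.

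**The concern.** Take two patients who both attend V2 without seizure data. One reports no seizures afterwards and is removed from the risk set at Visit 1. The other has a seizure recorded at Day 150 and stays in the analysis as an event. Their data up to V2 are the same, and only the later record separates them. Kaplan-Meier requires that, given the history so far, being censored tells us nothing about future events. Here it tells us that no seizure will be recorded.

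The unobserved time is real. Under SAP 4.2.1 the physician enters the number of seizures since the previous visit, so a V3 count need not cover a blank V1 to V2 interval.

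The median, quartiles and every monthly estimate of one secondary variable are at stake.

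**Working it through.** The plan states no figure for this variable, so there is none to reproduce.

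**Hand example (all inputs assumed).** 100 patients. The first seizure comes by Day 90 in 30, between Day 90 and Day 360 in 30, and never in 40. V2 seizure data are missing at random in 20, who split 6, 6 and 8. Early seizers have a further dated seizure after V2. There are no other gaps. The truth is 70% seizure-free at Day 90 and 40% at Day 360.

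1. *SAP rule, post-gap seizure used at its date.* The 8 never-seizers with a gap leave at Visit 1, so 92 are at risk. Day 90: 1 − 24/92 = 73.9%. Then 68 are at risk with 24 + 6 + 6 = 36 events. Day 360: 73.9% × (1 − 36/68) = 34.8%.
2. *SAP rule, post-gap seizure backdated to first dose.* There are 12 events on Day 1 and 8 censored that day: 1 − 12/100 = 0.88. Then 24 of 80 have events. Day 90: 0.88 × 56/80 = 61.6%. Day 360: 61.6% × 32/56 = 35.2%. If Visit 1 precedes the first dose, the figures are 56/92 = 60.9% and 32/92 = 34.8%.
3. *Everyone with the gap censored at Visit 1.* Day 90: 1 − 24/80 = 70%. Day 360: 70% × (1 − 24/56) = 40%. Both match the truth.
4. *As 3, but keeping as events the 6 whose first seizure is known to lie inside the gap.* 14 are censored and 86 are at risk. Day 90: 1 − 30/86 = 65.1%. Day 360: 65.1% × 32/56 = 37.2%. The bias returns, because a gap patient is kept only if he or she had a seizure in the gap.

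**Simulation (inputs assumed).** Seizure data are missing completely at random at attended visits, with visits at Days 90, 180 and 360. All seizures are dated, and a post-gap seizure is used at its date. Process A: 30% never seize and the rest follow a gamma-Poisson process (shape 0.6) with mean 2 seizures per 28 days. Process B: 50% never seize, mean 1. A and B have no discontinuation and 30,000 patients each. Process C (20,000 patients): gamma Baseline rates with mean in the range 1.5 to 3 per 28 days, and an on-treatment rate 60% of Baseline. Entries are % seizure-free: true / SAP rule / uniform censoring at the first gap.

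| Process | Missing per visit | Day 90 | Day 360 |
|---|---|---|---|
| A | 5% | 46.3 / 48.0 / 46.5 | 37.4 / 36.0 / 37.6 |
| A | 10% | 45.5 / 49.1 / 45.7 | 36.8 / 33.4 / 37.0 |
| A | 20% | 45.4 / 52.4 / 45.8 | 37.0 / 29.0 / 37.4 |
| B | 5% | 66.4 / 67.2 / 66.5 | 57.6 / 55.9 / 57.6 |
| B | 10% | 66.5 / 67.8 / 66.5 | 57.7 / 54.1 / 57.6 |
| C | 10% | 13.5 / 21.7 / 13.6 | 2.9 / 2.4 / 3.0 |

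For C at 5% missing, Day 90 is 17.5% against a true 13.4%. The Day 90 error is thus 0.8 (B) to 4.1 (C) points at 5% missing and 1.3 (B) to 8.2 (C) at 10%. The median in A at 10% missing is 80 days under the SAP rule, against 57 true and 58 with uniform censoring.

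A separate run (30% never seizing, 10% missing) compared the other rules. True Day 90 was 46.2% and true Day 360 was 37.2%. Using the seizure date gave 49.6% and 33.8%. Backdating gave 43.5% at Day 90. Uniform censoring gave 46.3% and 37.4%. The in-gap exception of step 4 gave 43.7% and 34.4%.

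**Undated seizures.** In process A at 20% missing, backdating puts so many events on Day 1 that the median becomes Day 1. The Day 360 error then depends on timing: 37.4% against a true 37.8% if Visit 1 censoring ties with Day 1, but 33.0% against 37.5% if Visit 1 precedes the first dose.

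**The case against.** The best reply is that a seizure date recorded after an unobserved interval is not known to be the first, so its exact date cannot be determined and Table 8-2 backdates it. On that reading no gap time counts as seizure-free, and the early curve errs low, as the SAP's description of its approach as conservative implies. This stands against one inference that a reader might draw: that the plan always makes early seizure freedom look too good. The documents do not support that, because they do not settle which reading applies. The reply does not rescue the rule, though. M followed by a positive count is still an event while M/0/0 is censored, and the late curve is still too low.

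Missing data are also limited by design. A diary is an entry criterion (Protocol 8.1), the physician interviews the patient to fill in missing information (Protocol 11), and a wholly missed visit can be recovered at the next one (SAP 4.2.1). That may keep the affected share small, but no figure is given. If the CRF first-seizure field is known to cover the gap for all patients, the gap is not missing information for this variable. The CRF layout is not in the documents.

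The optional sensitivity analysis is a partial answer at best. Without a trigger or method, it leaves the main estimate as it is.

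Finally, a 2-point error is smaller than sampling error: at 46% with 385 patients the 95% half-width is 1.96 × √(0.46 × 0.54/385) = 0.050. That bears on priority. It does not make the rule right, since bias does not shrink with sample size.

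**Conclusion.** Wrong as written. Censoring for missing seizure data is decided by the later outcome, so the Kaplan-Meier estimates of time to first seizure are biased even under completely random missingness. The early direction depends on how a dated seizure after a gap is treated: too high if used at its date, too low if backdated. With dated seizures the late curve is too low under both. The size is about 1 to 4 points at 5% missing and 1 to 8 at 10%. These ranges come from Day 90 with the date used as recorded, and they rest on assumed seizure processes and an assumed missing rate.

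A reader might infer that the study's main result is affected. It is not: 12-month retention (SAP 8.1.1) is derived from dosing and termination dates. This variable is secondary, and SAP 3.1 makes all analyses descriptive.

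**What to change.** For every patient, before looking at later records, censor at the last visit before the first attended visit with missing seizure data, unless a seizure is recorded before that point. Put the Table 8-2 event rows that follow an M (M/M/>0, M/>0, M/-/>0 and -/M/>0) under the same rule. This also settles M/0/>0 and 0/M/>0, which have no event row now.

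Do not add an exception that keeps only patients whose first-seizure date falls inside the gap. If the CRF field is known to cover the gap for all patients, including those without a seizure, treat the interval as observed for everyone and do not censor.

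Backdating of undated seizures is a separate distortion that this change does not remove. In process A at 20% missing with undated seizures, uniform censoring tied with Day 1 gave 48.2% at Day 360 against a true 37.5%. Specify an interval-censored sensitivity analysis for this and make it mandatory, or give it a stated trigger. Report the number of attended visits without seizure data.

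The cost is SAP wording, a reordered derivation, fewer events and slightly wider intervals. No new data are needed.

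### Time to first seizure uses different end dates for events and for censoring in patients who stop BRV, and can credit time with no seizure data as seizure-free

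*SAP*

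**What the plan says.** Protocol 4.2 defines the secondary variable as "Time to first seizure after first dose of BRV", with no cut-off when BRV stops. SAP 8.2.3 computes it as "Date of first seizure in the trial – date of first BRV administration + 1". If seizures are recorded but the first is undated, "then the patient will still be counted as having an event using a conservative approach".

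The censoring rules have a restricted scope: "For patients with no evidence of seizures, the following sequential approach will be taken". In order:

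- Rule 1, visit attended without seizure data: "they will be censored at the date of the last visit prior to the visit with the missing seizure information".
- Rule 2, BRV stopped with no seizure so far: "they will be censored at the date of last administration of BRV while in the study".
- Rule 3, still on BRV with no seizure: censored at the last visit.

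Table 8-2 has two rows for stopping BRV. `0 | Disc BRV | NA` is censored at last BRV, and `M | Disc BRV | NA` at Visit 1. The key reads "NA=Visit is not applicable/not required to be considered in this scenario" and "M=patient is missing seizure data at this visit but attended the visit". A wholly missed visit has its own symbol, a dash, which appears only on the side of the table where seizures were recorded.

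**The concern.** Kaplan-Meier estimation needs every patient in the risk set to be under observation, and one rule for when observation ends whether or not an event occurs. Rule 2 can break both conditions.

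**Mechanism A.** The last-dose date comes from the termination page or, failing that, the BRV medication page (SAP 3.2.4). It can exist with no visit and no diary review behind it. Such a patient stays in the risk set but cannot contribute an event, which pushes the curve up.

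**Mechanism B.** After the last dose, a recorded seizure is an event, while recorded seizure-free time is discarded. That pushes the curve down.

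At stake is a secondary Kaplan-Meier curve, with its median and quartiles, whose position would partly reflect how dropouts were followed.

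**Working it through.** **The rules applied to example patients** (days chosen for illustration)

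| Patient | SAP result | Comment |
|---|---|---|
| 0 at Visit 2 (Day 90), last BRV Day 170, no further visit | censored Day 170 | 170 - 90 = 80 days without data |
| No visit after Baseline, last BRV Day 100 | no table row; rule 2 gives Day 100 | no post-Baseline data at all; Table 8-1 sets Month 3 seizure freedom to missing by both methods |
| 0 at Visit 2, stops BRV, withdrawal visit attended, count missing | rule 1: Visit 2; table row: last BRV | the two conflict |
| Visit 2 attended, count missing, then stops BRV | Visit 1 | protected |
| Last BRV Day 170, seizure Day 185, withdrawal visit Day 200 | event Day 185 | 15 days off BRV |
| The same without a seizure | censored Day 170 | 30 observed days dropped |

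Rule 2 describes patients who stop before their first seizure, so the fifth patient could also be read as censored. The text does not settle it. An undated seizure is also moved back: `0 | - | >0` becomes an event at Visit 2, which can place a seizure after BRV stop at a time on BRV.

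**Planning figure.** None exists for this variable. The only one is the FAS size in SAP 2.4: 1.96² × 0.25 / 0.05² = 384.1, rounded up to 385, which reproduces. Its proportion of 0.50 is borrowed below as a retention value; it is not a forecast.

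**Size, by simulation.** 300,000 patients per scenario. Assumed, not in the documents: retention 0.50 or 0.70; 15% (median 14 days) or 20% (medians 30 and 90 days) seizure-free on BRV, the rest with exponential first-seizure times at those medians; stopping unrelated to seizures. Let q be the share of dropouts with no withdrawal seizure data, and gap the days from last BRV to the withdrawal visit. Shifts are SAP rule minus true on-BRV curve at Day 330, retention 0.50.

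| Median of those who seize | A: q = 50%, gap 0 | B: q = 0, gap 30 days | Both |
|---|---|---|---|
| 14 days | +4.0 | 15.0% to 8.8% (-6.2) | -0.3 |
| 30 days | 20.0% to 22.6% (+2.6) | 20.0% to 14.3% (-5.7) | -0.8 |
| 90 days | 26.4% to 29.1% (+2.7) | 26.4% to 22.9% (-3.5) | +0.8 |

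- Curve median under A: 18 to 21, 43 to 48 and 128 to 138 days. Under B: 18 to 18, 43 to 41 and 128 to 118 days.
- A with q = 25%: +1.3 to +2.0 points. With q = 100%: +5.4 to +8.0.
- Retention 0.70: +1.3 to +2.0 (A, q = 50%) and -1.8 to -3.5 (B, 30 days).
- The near-cancellation is specific to Day 330. At Day 90 the combined shift is +2.9, +1.6 and +0.6 points (16.0 to 18.9, 29.8 to 31.4, 60.0 to 60.6).
- q = 0 and gap 0: no shift.

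**Hand check of B.** With a constant stopping rate that leaves 50% on BRV at Day 330, and p = 1 - 2^(-30/median) the chance of a seizure in the gap, each stopper becomes an event with probability p, so the curve is multiplied by 0.50^p. For p = 0.774, 0.500 and 0.206:

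- 15.0 × 0.585 = 8.8
- 20.0 × 0.707 = 14.1
- 26.3 × 0.867 = 22.8

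This agrees with the table and exposes an assumption: every stopper, including one who would have stayed seizure-free on BRV, seizes at that rate once off BRV. If those patients stayed seizure-free, the multiplier would be S^(p × median/330), with S the true Day 330 proportion:

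- 0.150^0.0328 = 0.940, giving 14.1 (-0.9)
- 0.200^0.0455 = 0.929, giving 18.6 (-1.4)
- 0.263^0.0563 = 0.928, giving 24.4 (-1.9)

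**Fix tested.** Ending both events and censoring at the earlier of last BRV and the last date covered by seizure data recovers the true on-BRV curve to within about 0.1 point at Days 90, 180 and 330.

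**The case against.** The rules are sequential. Rule 1 precedes rule 2, and `M | Disc BRV` gives Visit 1, so patients who attended without seizure data are already handled cautiously. Protocol section 5 asks for a Withdrawal Visit with Visit 4 data, so many dropouts should have seizure data near their last dose. Under Protocol 8.2, stopping BRV permanently means leaving the study, which limits the gap. If neither the termination page nor the medication page gives an end date, SAP 3.2.4 falls back to the first dose, so such a patient is not credited with unobserved time. The variable is descriptive, and the by-patient listing shows the relevant dates. All of this stands and narrows the point.

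A reader might infer more than the documents support:

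- **That the curve is wrong for dropouts.** It can be biased. The share without withdrawal data and the gap length are not given, and the error is zero when coverage is complete.
- **That stoppers are treated oppositely to patients still on BRV.** `M | M | M` and `M | Disc BRV` both give Visit 1. The unprotected group is dropouts with no withdrawal visit.
- **That counting a seizure after BRV stop is an error.** It fits the protocol variable. The fault is pairing it with censoring at last BRV.

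The possible offset is no defence, because it depends on follow-up and on the time point. Nor does the optional sensitivity analysis in 8.2.3 help: it is prompted by many early censorings or early events from missing data, whereas mechanism A censors too late.

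**Conclusion.** The point holds in this limited form. Rule 2 and the row `0 | Disc BRV | NA` have no data-coverage condition; rule 1 and that row conflict for a withdrawal visit attended without seizure data; BRV stop before Visit 2 has no row; and events and censoring end at different dates.

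Under the stated assumptions the shifts at Day 330 are a few points: about +2.6 to +4.0 (A, half of dropouts uncovered) and -3.5 to -6.2 (B, 30-day gap) at retention 0.50, and about half that at 0.70. The range for B rests on all stoppers seizing at the assumed rate; otherwise it is about -0.9 to -1.9. The net direction cannot be determined from the documents. Primary retention does not use this derivation. The point should be corrected, but it does not threaten the study's main result.

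**What to change.** In SAP 8.2.3 and Table 8-2:

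1. State one target: seizures on BRV, or seizures regardless of BRV stop, as the protocol wording suggests. If on-BRV is chosen, declare the narrowing.
2. Use the same end date for events and censoring.
3. Never censor later than the last visit up to which seizure data are continuously recorded (Day 1 if none). Keep rule 1's precedence and the row `M | Disc BRV`, censored at Visit 1. Referring simply to the last visit with data would override rule 1 when an earlier visit lacks data.
4. Replace `0 | Disc BRV | NA`, censored at last BRV, accordingly. Add rows for missed visits on the no-seizure side and for BRV stopped before Visit 2.
5. If the on-BRV target is chosen, say how undated seizures first recorded at a visit after BRV stop are handled, since the table moves them back to an earlier visit.

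The simulation did not cover earlier visits with missing data, undated seizures or the regardless-of-stop target, so items 3 and 5 rest on the logic of the rules. The cost is SAP wording and one derivation from dates already collected; the seizure-free curve may look slightly less favourable.
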